2.1. Definitions

The **full analysis set** will consist of all randomized participants who received at least one day of intervention. If participants withdraw informed consent after baseline assessment, they will be considered screening failures and, therefore, will not be included in the full analysis set. The

per-protocol analysis set comprises all subjects who received the full three weeks of intervention or control intervention and completed all visits in the treatment groups they were allocated to. Safety outcomes [see Safety outcomes section (22)] are assessed during tDCS intervention, and all participants who received at least one intervention will be included in the safety analysis set according to their actual treatment. Since no participant received other treatment as intended or switched treatment groups during the study, and no information on safety measures is available for participants who missed intervention or follow-up visits or dropped out, the safety analysis set is the same as the per protocol analysis set in this study.

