2.2. Application

The primary efficacy analysis will be done using the full analysis set, including estimated values from multiple imputations for missing values (Intention to treat). A sensitivity analysis of the primary outcome in the per-protocol analysis set will be conducted. The safety analysis will be done in the safety analysis set, which is the same as the per-protocol analysis set.

3. Trial centers

Participant recruitment takes place at one center: Universitätsmedizin Greifswald.

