4.1. Primary outcome

Untrained working memory performance at post-assessment, measured by the percentage of correct responses on the n-back task (23).

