4.3. Safety outcomes

Safety is assessed through an adapted (22) self-report questionnaire administered every third training day (V4, V7 and V10). This questionnaire asks participants to rate the intensity of various sensations, including itching, pain, burning, warmth/heat, metallic or iron taste, fatigue, decreased alertness, and others.

Table 1. Neuromod-COV outcome measures	. Adapted from Neuromod-COV	/ study protocol (14).
--	-----------------------------	------------------------

			Baseline	Pre (3 days before T1)	T1-T9 (9 sessions for 3 weeks)	Post (3 days after T9)	FU (1 month after Post)
			$\sim 3h$	~ 3h	~ 1h	~ 3h	~ 3h
Time point	Measurement	Mode	V0	V1	V2-V10	V11	V12
Enrollment							
Informed consent		Paper	Х				
Eligibility	Medical history	Paper	Х				
screening	Mini-DIPS (30)	Paper	Х				
Questionnaires	Demographics	Paper	Х				
Neuropsychological screening	VLMT (23) ROCF (31) DS (32) TMT(23) Stroop (33) PF (23) SF (23)	Paper	Х				
Intervention					← →		
Training tasks	Letter updating task (24)	Tablet-PC	Х	X	x ^a	Х	x
	PMR (18)	Instructed			x ^b		
Brain stimulation	tDCS (anodal vs. sham)	Device			х		

	Initial state questionnaire	Paper	X	Х	х	Х	Х
Quastiannairas	PANAS (34)	Paper			Х		
Questionnaires	Adverse events questionnaire ^c (22)	Paper			Х		
Additional assessm	nents						
Linturin ed te elve	n-back task (23)	Computer		Х		X ^d	Х
Virtual	Virtual reality task (25)	Computer		Х		Х	Х
	PROMIS® (29-Profile v2.1 & Cognitve functioning SF 8a v2.0; 28)	Paper		х		x	х
Questionnaires	Sleeping behavior: PSQI (35) ESS (36) MEQ (37)	Paper		x		x	х
	PCFS (29)	Paper		Х		Х	Х
General activity	Actigraphy	Device		х		Х	

T1-T9: trainings 1-9; FU: follow-up assessment; V0-V12: visits 0-12; Mini-DIPS: Brief Diagnostic Interview for Psychiatric Disorders; VLMT: German version of the auditory verbal learning test; ROCF: Rey-Osterrieth Complex Figure Test; DS: Digit Span Test; TMT: Trail Making Test. Stroop: Stroop Test; PF: Phonological fluency; SF: Semantic fluency; PMR: Progressive Muscle Relaxation; tDCS: transcranial Direct Current Stimulation.

PANAS: Positive and Negative Affect Schedule; PROMIS®: Patient-reported Outcome Measurement Information System; PSQI: Pittsburgh Sleep Quality Index; ESS: Epworth Sleepiness Scale; MEQ: Morningness-Eveningness Questionnaire; PCFS: Post-COVID Functional Scale.

^a Only for cognitive training groups.

^b Only for the PMR group.

^c Assessed every third training day (V4, V7 and V10).

^d Primary outcome

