5. Handling of missing values

In cases of missing data and assuming the data are missing at random (MAR) or completely at random (MCAR), multiple imputation will be used to estimate the missing values with 30 imputed datasets.

6. Statistical analyses

For all outcomes and time points, we will present appropriate descriptive statistics (mean, standard deviation, median, interquartile range, and absolute and relative frequencies) depending on the scale and distribution of each outcome variable in total (only at preassessment) and by group. The statistical analyses will evaluate the immediate treatment effects at post-assessment (V11) and the sustained treatment effects at the one-month follow-up assessment (V12). In the secondary analyses, we will compare the cognitive training and groups, as well as the cognitive training groups receiving active versus sham tDCS.

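### The per-protocol set requires the one-month follow-up visit, so the sensitivity analysis of the V11 primary outcome drops fully treated participants who have valid V11 data

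*SAP*

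**What the plan says.** SAP Section 2.1 sets two joint conditions for the per-protocol set: the full three weeks of intervention or control, and having "completed all visits in the treatment groups they were allocated to". Table 1 (Section 4.3) numbers the visits in its footnote as "V0-V12: visits 0-12". Post-assessment is V11, three days after the last training session; follow-up is V12, one month after that.

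Section 4.1 defines the primary outcome as "Untrained working memory performance at post-assessment, measured by the percentage of correct responses on the n-back task". Section 2.2 then states: "A sensitivity analysis of the primary outcome in the per-protocol analysis set will be conducted". No other sensitivity analysis of the primary outcome is planned. The closing paragraph of Section 6.2 also makes per-protocol analyses the sensitivity analyses for the secondary outcomes.

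The primary analysis itself uses the full analysis set with multiple imputation (Section 2.2). Section 6.1 fits post and follow-up n-back scores in one linear mixed model with a random intercept for subjects, and Section 6.2 takes the follow-up effect from the same fit.

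**The concern.** A per-protocol analysis of a V11 outcome should ask what happens among people who received the allocated treatment and were measured at V11. Here membership also depends on attending a visit a month after the outcome was recorded. If attendance at V12 is related to the V11 result, or to how the participant judged the intervention, the restriction itself creates selection. A difference between the per-protocol and full-set results could then come from non-adherence or from V12 loss, and the reader could not tell which.

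The same rule reaches every V11 secondary outcome. Sleep efficiency shows this most plainly: it is not measured at V12 at all (Section 4.2, Table 1), yet its per-protocol analysis would exclude people for missing V12.

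**Working it through.** **1. Does the rule reach V12?** Section 2.1 says all visits; Table 1 ends at V12; nothing restricts the phrase to visits up to V11. When Section 2.1 equates the safety set with the per-protocol set, it places people who missed intervention or follow-up visits outside that set, which supports the same reading.

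**2. Does the V11 estimate need V12?** No. In a random-intercept mixed model (Section 6.1), a participant with V11 scores and no V12 score still contributes. The exclusion gains nothing for the primary time point.

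**3. The plan's own figure.** Section 1.4: d = 0.8, two-sided alpha 0.05, 40 vs 20, independent t-test. The non-centrality is d × √(n₁n₂/(n₁+n₂)) = 0.8 × √(800/60) = 2.92 on 58 degrees of freedom, giving power 0.819. The stated 60 participants for at least 80% power is reproduced.

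**4. How many could be lost.** The SAP gives no rate of V12-only loss. Assume 60 V11 completers and proportional loss q; the standard error grows by 1/√(1−q).

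| Assumed V12-only loss | Per-protocol n | SE ratio |
|---|---|---|
| 0% | 40/20 | 1.00 |
| 10% | 36/18 | 1/√0.9 = 1.054 |
| 20% | 32/16 | 1/√0.8 = 1.118 |

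Each PMR participant lost is 1/20 = 5% of that arm.

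**5. How far selection could move the estimate.** All inputs in this step are assumed except d = 0.80. Scores have SD 1. The probability of missing V12 follows logit P = logit(0.12) − ln(OR) × z, where z is the V11 score in SDs from the PMR mean and OR is 1.6 or 2.7. In the PMR-only rows, loss in the training arm is random at 10%. Estimated d by simulation:

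| Where loss depends on the score | Analysis | OR 1.6 | OR 2.7 |
|---|---|---|---|
| PMR only | Unadjusted | 0.74 | 0.66 |
| PMR only | Baseline-adjusted, pre/post correlation 0.5 | 0.76 | 0.70 |
| PMR only | Baseline-adjusted, correlation 0.7 | 0.77 | 0.73 |
| Both arms | Unadjusted | 0.78 | 0.74 |
| Both arms | Baseline-adjusted, correlation 0.7 | 0.79 | 0.77 |

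The planned model adjusts for pre-assessment n-back, so the adjusted rows are closer to what would be run. The direction is also assumed: if high scorers in PMR were the ones to skip V12, the shift would be upward. With random loss, or loss that moves both arm means equally, the expected estimate stays at 0.80.

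**The case against.** Requiring all visits is a conventional completer definition, and a single completer set fits a model that estimates V11 and V12 together. The SAP does not contradict itself here. Any per-protocol analysis also selects on post-randomisation events, since completing nine sessions is one. These points stand, and they keep the matter small. They do not justify the V12 condition, because the joint model can use V11-only participants and this part of the selection is avoidable.

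A reader might infer that the primary result is biased or loses valid data. The SAP does not support that: the primary analysis is in the full analysis set with multiple imputation, and missing V12 excludes nobody from it.

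A reader might also argue from power, since the t-test figure at d = 0.8 falls from 0.819 to 0.776 (36/18) or 0.725 (32/16). That breaks nothing the plan promises. Section 1.4 powers the trial on 40 vs 20, not on the per-protocol set, and a sensitivity analysis carries no power claim.

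Finally, quoting only the unadjusted, PMR-only shift (0.74 and 0.66) would overstate the likely bias. Baseline adjustment, or the same dependence in both arms, reduces it.

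**Conclusion.** The point holds as a defect of the sensitivity analysis only. As worded, Section 2.1 removes fully treated participants with valid V11 scores from the per-protocol analysis of the V11 primary outcome and of V11 secondary outcomes, and it selects on attendance after the outcome.

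The size is unknown. It is zero if nobody misses V12 alone. Under the assumed outcome-dependent loss, a true d of 0.80 would be estimated at about 0.66 to 0.79. That range rests on the 12% base rate, the odds ratios of 1.6 to 2.7, the direction of the dependence and the assumed pre/post correlation, none of which the SAP supplies. The documents do not show that any such loss occurred or that it relates to the V11 score. This is a cheap improvement, not a threat to the trial's main conclusion.

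**What to change.** In Section 2.1, define the per-protocol set as participants who completed the allocated three-week intervention and have the V11 assessment, without requiring V12. Keep one set and fit the Section 6.1 model once in it, with V12 scores contributing where they exist. Separate sets for V11 and V12 would mean fitting the joint model twice or stating which fit supplies which estimate.

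Sections 2.1 and 2.2 declare the safety set identical to the per-protocol set, so this change would carry over to it. State the safety set by the rule Section 2.1 already gives (at least one intervention received, analysed by actual treatment) and drop the identity. The safety questionnaire is administered at V4, V7 and V10, so attendance at V12 has no bearing on whether those data exist.

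The cost is a short edit to Sections 2.1 and 2.2. The number observed will differ between V11 and V12 in the per-protocol tables and should be shown for each visit. Per-protocol V12 estimates will rely on the model's missing-at-random assumption. Nothing about treatment, visits or data collection changes.

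### The safety set is defined as everyone treated at least once and then equated with the all-visits per-protocol set; the two agree only if every treated participant completed every visit

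*SAP*

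**What the plan says.** Section 2.1 of the SAP gives two descriptions of the safety set. The first is based on treatment received: "all participants who received at least one intervention will be included in the safety analysis set according to their actual treatment". The second follows directly: "the safety analysis set is the same as the per protocol analysis set in this study". The per-protocol set, defined just before, "comprises all subjects who received the full three weeks of intervention or control intervention and completed all visits" in the allocated group.

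Two reasons are given for treating the sets as one. Nobody switched or received a treatment other than the intended one, and "no information on safety measures is available for participants who missed intervention or follow-up visits or dropped out".

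Section 2.2 repeats the equality and applies it: "The safety analysis will be done in the safety analysis set, which is the same as the per-protocol analysis set".

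Three other places bear on the point:

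- The full analysis set is "all randomized participants who received at least one day of intervention" (section 2.1), and section 2.2 plans a separate per-protocol analysis: "A sensitivity analysis of the primary outcome in the per-protocol analysis set will be conducted".
- Section 4.3 and Table 1 schedule the safety questionnaire at V4, V7 and V10. Training sessions run from V2 to V10, the post-assessment is V11 and the follow-up is V12.
- Section 6.3 plans Poisson models for safety incidence that allow for unequal observation periods.

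**The concern.** A set of all treated participants and a set of completers are different populations unless completion was perfect, and the SAP does not assume that it was. It refers to participants who missed visits or dropped out, it imputes missing values, and it plans a per-protocol analysis alongside the full-set analysis. With one treated non-completer, the two descriptions of the safety set cannot both be followed.

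The choice fixes the denominator of every safety table, including the comparison of active with sham tDCS. Under the equality, a treated participant who did not finish contributes imputed values to efficacy and nothing to safety. If any of these participants stopped because they tolerated the sessions badly, the safety results lose the people who matter most. A reader who sees a set labelled as everyone treated at least once would not know that it holds only completers, or how many are missing.

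**Working it through.** The SAP states no figure for this point, so there is none to reproduce. The check uses the definitions, the visit schedule and the planned arm sizes.

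**1. Set logic.** Let S be everyone treated at least once, and PP everyone with the full three weeks and all visits in the allocated group. PP is a subset of S. The no-switching statement removes only the difference between actual and allocated treatment. After that, S = PP if and only if no treated participant missed a session or visit. As an illustration, assume all 60 planned participants start treatment:

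| Assumed share missing any session or visit | S | PP | Treated but left out |
|---|---|---|---|
| 0% | 60 | 60 | 0 |
| 5% | 60 | 57 | 3 |
| 10% | 60 | 54 | 6 |
| 15% | 60 | 51 | 9 |
| 20% | 60 | 48 | 12 |

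**2. Does the stated lack of data fit the schedule?** Sessions are V2 to V10 (nine), with questionnaires due at V4, V7 and V10 (three).

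| Last session attended | Questionnaires due |
|---|---|
| V2, V3 | 0 |
| V4, V5, V6 | 1 |
| V7, V8, V9 | 2 |
| V10 (then misses V11 or V12) | 3 |

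There are eight early-stopping points, V2 to V9. At six of them, V4 to V9, at least one questionnaire had already fallen due. This counts visits, not people. In addition, 9 − 3 = 6 sessions are not questionnaire visits. Missing one of these alone, if it is not made up, loses no questionnaire but removes the participant from PP. So even a narrower rule, treated with at least one questionnaire, would not reproduce PP if these questionnaires were completed.

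**3. What the exclusion leaves open.** Sixty participants at 1:1:1 (sections 1.1 and 1.4) give 20 per arm. If m is the fraction of treated participants left out of an arm, then

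incidence in all treated = (1 − m) × incidence in completers + m × incidence in those left out.

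The last incidence can lie anywhere from 0 to 1, so the undetermined width equals m:

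- one participant left out: 1/20 = 5.0 percentage points of that arm (1/60 = 1.7 points overall);
- four left out: 4/20 = 20 points.

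One to four per arm is an assumed range. The bound applies to the proportion of participants with an event, not to Poisson rates or rate ratios.

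**4. Section 6.3.** In a set of completers, everyone has the same scheduled sessions and questionnaires. There is then little or no scheduled difference in observation period for the Poisson models to account for. That provision makes more sense for S than for PP.

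**The case against.** The strongest reply is that the SAP equates the sets on a factual ground and not by definition alone. If no safety information exists for anyone who missed a visit, then the treated participants with analysable safety data are the completers, and no rule can add ratings that were never collected. The defect would then be one of labelling and transparency. The schedule shows which questionnaires were due, not which exist, so the SAP's statement cannot be refuted from the document.

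That much stands: the statement is doubtful, not disproved, and if it is true the incidence estimates would not change. It does not rescue the equality. The definition turns on treatment received, so a treated participant without a questionnaire is a treated participant with missing safety data and still belongs in the set. The statement also covers people who missed only follow-up visits, and for them all three questionnaires had already fallen due.

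Some smaller points are fair:

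- The full analysis set may not match the safety definition exactly, because participants who withdraw consent after baseline are treated as screening failures.
- Planning a per-protocol sensitivity analysis is routine and only weak evidence that the sets differ. The SAP's own mention of missed visits and dropouts is the better evidence.
- Observation period is not defined in section 6.3, so completers could still differ somewhat, for example through unreturned questionnaires.
- The case of a single missed session assumes that sessions were not made up, which the SAP does not say.

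None of these removes the contradiction between the two descriptions of the safety set.

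**Conclusion.** The concern holds, and the SAP must be corrected. Sections 2.1 and 2.2 give two incompatible safety sets unless every treated participant completed every visit, and the SAP's own text does not assume that.

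Neither the size nor the direction of any bias can be derived, because the number of non-completers and their reasons for stopping are not given. The 5 to 20 percentage points per arm rest on an assumed one to four exclusions among 20 planned. They bound what is unknown and do not estimate bias. The bias is zero if non-completers have the same risk as completers, and any questionnaires that do exist for them would narrow the bound.

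**What to change.** - In sections 2.1 and 2.2, delete the statements that equate the safety set with the per-protocol set. Keep the definition already written: everyone who received at least one intervention, by actual treatment.
- In section 6.3, state that every available V4, V7 and V10 questionnaire is used, with the number completed per participant as the exposure offset in the Poisson models.
- Report by arm how many treated participants contributed no safety data.
- If no questionnaire exists for any non-completer, say so, and show these participants as treated with missing safety data.

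The cost is SAP wording, plus producing (or re-running) the safety tables with whatever questionnaires exist for non-completers. If there are none, the change comes down to one sentence and a count by arm. No new data collection is needed.

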2.2. Application

The primary efficacy analysis will be done using the full analysis set, including estimated values from multiple imputations for missing values (Intention to treat). A sensitivity analysis of the primary outcome in the per-protocol analysis set will be conducted. The safety analysis will be done in the safety analysis set, which is the same as the per-protocol analysis set.

3. Trial centers

Participant recruitment takes place at one center: Universitätsmedizin Greifswald.

3.1. Recruitment

Patients are recruited from the post-COVID-19 outpatient clinic at the *Universitätsmedizin* Greifswald. We also search for participants by distributing flyers to local post-COVID support groups and placing announcements in the local newspaper. Interested participants are provided with detailed information about the study, both orally and in writing. All potential participants undergo a telephone screening, where study details are also explained. Those who meet the eligibility criteria are invited to attend a baseline assessment. The recruitment process is shown in the CONSORT flow diagram (Figure 1).

4. Analysis variables

All measures are detailed below in Table 1.

4.1. Primary outcome

Untrained working memory performance at post-assessment, measured by the percentage of correct responses on the n-back task (23).

4.2. Secondary outcomes

Secondary outcomes will be assessed at both post-assessment and follow-up with specific exceptions indicated by an asterisk (*). These include:

- Untrained working memory performance, measured by the percentage of correct responses on the n-back task [(23) *at follow-up assessment].
- Trained working memory performance, measured by the number of correctly recalled lists on the letter updating task (24).

Statistical Analysis Plan

"Neuromodulation through brain stimulation-assisted cognitive training in patients with post-COVID-19 cognitive impairment (Neuromod- COV): study protocol for a PROBE phase IIb trial" Acronym: Neuromod-COV

- Untrained visuospatial memory performance, measured by the number of reached goals on the virtual reality task (25).
- Working memory discrimination, measured by the d-prime scores on the n-back task (23,26).
- Health-related quality of life, measured by the PROPr scores (27) on the PROMIS® 29-Profile v2.1 (28).
- Subjective cognitive functioning, measured by the T-scores on the PROMIS® Cognitive Function Scale [short form 8a v2.0; (28)].
- Post-COVID functional status, measured by the total raw scores on the PCFS (29).
- Sleep efficiency levels, measured as the percentage of time spent asleep relative to total time in bed, as recorded by an actigraphy device (*at post-assessment).

4.3. Safety outcomes

Safety is assessed through an adapted (22) self-report questionnaire administered every third training day (V4, V7 and V10). This questionnaire asks participants to rate the intensity of various sensations, including itching, pain, burning, warmth/heat, metallic or iron taste, fatigue, decreased alertness, and others.

Table 1. Neuromod-COV outcome measures	. Adapted from Neuromod-COV	/ study protocol (14).
--	-----------------------------	------------------------

			Baseline	Pre (3 days before T1)	T1-T9 (9 sessions for 3 weeks)	Post (3 days after T9)	FU (1 month after Post)
			$\sim 3h$	~ 3h	~ 1h	~ 3h	~ 3h
Time point	Measurement	Mode	V0	V1	V2-V10	V11	V12
Enrollment							
Informed consent		Paper	Х				
Eligibility	Medical history	Paper	Х				
screening	Mini-DIPS (30)	Paper	Х				
Questionnaires	Demographics	Paper	Х				
Neuropsychological screening	VLMT (23) ROCF (31) DS (32) TMT(23) Stroop (33) PF (23) SF (23)	Paper	Х				
Intervention					← →		
Training tasks	Letter updating task (24)	Tablet-PC	Х	X	x ^a	Х	x
	PMR (18)	Instructed			x ^b		
Brain stimulation	tDCS (anodal vs. sham)	Device			х		

	Initial state questionnaire	Paper	X	Х	х	Х	Х
Quastiannairas	PANAS (34)	Paper			Х		
Questionnaires	Adverse events questionnaire ^c (22)	Paper			Х		
Additional assessm	nents						
Linturin ed te elve	n-back task (23)	Computer		Х		X ^d	Х
Virtual	Virtual reality task (25)	Computer		Х		Х	Х
	PROMIS® (29-Profile v2.1 & Cognitve functioning SF 8a v2.0; 28)	Paper		х		x	х
Questionnaires	Sleeping behavior: PSQI (35) ESS (36) MEQ (37)	Paper		x		x	х
	PCFS (29)	Paper		Х		Х	Х
General activity	Actigraphy	Device		х		Х	

T1-T9: trainings 1-9; FU: follow-up assessment; V0-V12: visits 0-12; Mini-DIPS: Brief Diagnostic Interview for Psychiatric Disorders; VLMT: German version of the auditory verbal learning test; ROCF: Rey-Osterrieth Complex Figure Test; DS: Digit Span Test; TMT: Trail Making Test. Stroop: Stroop Test; PF: Phonological fluency; SF: Semantic fluency; PMR: Progressive Muscle Relaxation; tDCS: transcranial Direct Current Stimulation.

PANAS: Positive and Negative Affect Schedule; PROMIS®: Patient-reported Outcome Measurement Information System; PSQI: Pittsburgh Sleep Quality Index; ESS: Epworth Sleepiness Scale; MEQ: Morningness-Eveningness Questionnaire; PCFS: Post-COVID Functional Scale.

^a Only for cognitive training groups.

^b Only for the PMR group.

^c Assessed every third training day (V4, V7 and V10).

^d Primary outcome

5. Handling of missing values

In cases of missing data and assuming the data are missing at random (MAR) or completely at random (MCAR), multiple imputation will be used to estimate the missing values with 30 imputed datasets.

6. Statistical analyses

For all outcomes and time points, we will present appropriate descriptive statistics (mean, standard deviation, median, interquartile range, and absolute and relative frequencies) depending on the scale and distribution of each outcome variable in total (only at preassessment) and by group. The statistical analyses will evaluate the immediate treatment effects at post-assessment (V11) and the sustained treatment effects at the one-month follow-up assessment (V12). In the secondary analyses, we will compare the cognitive training and groups, as well as the cognitive training groups receiving active versus sham tDCS.

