6.3. Safety analysis

Safety outcomes will be reported as incidence (n & rates with 95% CI) both overall and by intervention groups, based on the safety analysis set. Incidence rates and corresponding 95% CIs will be estimated using Poisson regression models, which account for different observation periods across participants. Group comparisons will be conducted using incidence rate ratios and their 95% CIs. The safety analysis results will be interpreted and discussed comprehensively, including minor differences between groups.

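### The safety rates in section 6.3 cover completers only: participants who stop before V4 have no scheduled form, and the forms of later stoppers are left out of the set

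*SAP*

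**What the plan says.** Table 1 in SAP section 4.3 places the intervention at V2 to V10 ("T1-T9 (9 sessions for 3 weeks"). The same section sets the safety assessment: "Safety is assessed through an adapted (22) self-report questionnaire administered every third training day (V4, V7 and V10". The table footnote to the adverse events questionnaire repeats the schedule ("Assessed every third training day (V4, V7 and V10"), and the table shows no form at early stopping.

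Section 2.1 makes three statements about who is analysed for safety:

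- Definition: "all participants who received at least one intervention will be included in the safety analysis set according to their actual treatment".
- Availability of data: "no information on safety measures is available for participants who missed intervention or follow-up visits or dropped out".
- Application: "the safety analysis set is the same as the per protocol analysis set in this study".

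The per-protocol set is narrow: the "per-protocol analysis set comprises all subjects who received the full three weeks of intervention or control intervention and completed all visits". Section 2.2 repeats that the safety analysis uses this set. For the analysis, section 6.3 says: "Incidence rates and corresponding 95% CIs will be estimated using Poisson regression models, which account for different observation periods across participants". It names no other safety source and no tabulation of discontinuations.

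**The concern.** The questionnaire asks about pain, burning, itching, fatigue and similar sensations, any of which could lead someone to stop. A participant who stops for such a reason is absent from the planned safety analysis. Missingness of that kind is informative, because the chance of being unobserved rises with the severity of what would have been observed.

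Two separate mechanisms produce the gap. The visit schedule leaves the first two sessions before any form is due. The set definition then removes the forms that later stoppers were due to complete. Section 6.3 would present the results as the incidence of sensations by intervention group, without saying that they apply only to people who finished. A tolerability comparison between active and sham tDCS, or between training and PMR, would carry the same restriction.

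**Working it through.** **Inputs.** Nine sessions at V2 to V10 and forms at V4, V7 and V10 (section 4.3, Table 1). Set definitions from sections 2.1 and 2.2. Arm size of 20: section 1.4 plans 40 training participants and 20 PMR participants, and section 1.1 allocates 1:1:1. The number of dropouts and their reasons are not in the SAP, so they are varied below as assumptions.

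**Step 1: which forms were due.** V2 is session T1, so visit Vn is session T(n-1). Hence V4 = T3, V7 = T6 and V10 = T9.

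| Last session or visit attended | Forms due by then | In the set as defined (at least one intervention) | In the set as applied (per-protocol) |
|---|---|---|---|
| Session 1 or 2 | none | yes | no |
| Session 3, 4 or 5 | V4 | yes | no |
| Session 6, 7 or 8 | V4, V7 | yes | no |
| All nine sessions, but V11 or V12 missed | V4, V7, V10 | yes | no |
| All sessions and visits | V4, V7, V10 | yes | yes |

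Only the first row is out of reach of the schedule. The next three rows are lost through the set definition. The fourth row is notable: someone who missed only a post-treatment visit was due all three forms, yet section 2.1 groups those who missed follow-up visits with the participants who have no safety data.

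**Step 2: consistency with section 6.3.** Everyone in the per-protocol set has, by schedule, the same nine sessions and the same three forms. A Poisson model that allows for differing observation periods then has little to adjust for. It would have a purpose if participants with partial exposure were included, as the definition in section 2.1 provides.

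**Step 3: possible size (assumed figures).** Take an arm of 20 in which k participants stop because of a sensation and everyone else completes, with a share r of completers reporting that sensation. The calculation uses shares of participants as a simple stand-in for the Poisson rates.

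- Observed share, completers only: r
- Share counting the stoppers: [r(20 - k) + k] / 20
- Shortfall: k(1 - r) / 20

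| k | r = 10% | r = 30% | r = 50% |
|---|---|---|---|
| 0 | 0 | 0 | 0 |
| 1 | 4.5 points | 3.5 points | 2.5 points |
| 2 | 9.0 | 7.0 | 5.0 |
| 3 | 13.5 | 10.5 | 7.5 |
| 4 | 18.0 | 14.0 | 10.0 |

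In whole people: if 2 of 20 stop for pain and 2 of the 18 completers report pain, the completers-only share is 2/18 = 11.1%, against 4/20 = 20% when the stoppers are counted.

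**The case against.** The strongest reply is that data collection belongs to the protocol, which is not at hand. Adverse event reporting and withdrawal contacts are commonly described there, and Table 1 is itself adapted from it. This stands as far as it goes: the questionnaire is the only safety instrument that this SAP names, and nothing more can be said about the trial as a whole. It does not rescue the analysis. Section 2.1 states that dropouts contribute no safety information, and section 6.3 draws on no other source.

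Several stronger readings are tempting and should not be drawn:

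- A reader might infer that intolerance ending treatment early can never be counted. By schedule this is true only of stops before V4.
- A reader might infer that tolerability is overstated. That requires someone to have stopped for intolerance, and the SAP does not say whether anyone did.
- A reader might say that six of the nine sessions go unassessed. That assumes each form covers only its own day; the recall period is not stated.
- A reader might describe the rates as conditional on reaching the third session. Under sections 2.1 and 2.2 they are conditional on completing every session and visit, which is narrower.

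It can also be said that the statement about missing data simply reports what happened, for instance that every dropout left before V4. The past tense in that part of section 2.1 makes this possible. If so, widening the set would add no forms, but the uncovered group would be exactly the early stoppers, and a table of stops with reasons would be the only safety information about them.

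**Conclusion.** The point holds in this form. The safety set is defined as all treated participants but applied as completers, and the first form is not due until the third session. The rates and rate ratios in section 6.3 therefore leave out everyone who did not complete, and they may understate intolerance.

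The conflict within section 2.1 and the visit-to-session mapping rest on the SAP's text alone. The size of any bias does not. It is zero if nobody stopped because of a sensation or adverse event. Under the assumptions above it runs from 2.5 points (one such stop, half of completers affected) to 18 points (four such stops, a tenth of completers affected) in an arm of 20. The efficacy analyses are not affected. This is an inexpensive improvement to the safety reporting, and worth making because each early stop is 1/20 = 5% of an arm.

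**What to change.** In sections 2.1, 2.2 and 6.3:

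1. Apply the safety set as defined, meaning everyone with at least one intervention, as treated. Remove the statement that it equals the per-protocol set. Use every available V4, V7 and V10 form from anyone treated.
2. Add a table by the three arms giving the number who stopped before V4, before V7 and before V10, with the recorded reason.
3. Add a sensitivity analysis that counts a stop recorded as due to a sensation or adverse event as an event.
4. State beside the results that the questionnaire rates do not cover participants who stopped before V4.

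If collection is still open, also give the existing form at the first session and at the last attended visit or discontinuation contact. The wording of section 2.1 suggests that this may no longer be possible; items 1 to 4 do not depend on it.

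The cost is one extra table and one sensitivity line. The safety figures may look slightly less favourable. Items 2 and 3 are only as informative as the reasons for stopping that were recorded.
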